9.3 Protocol Deviation

The number (n) and percentage (%) of participants presenting with at least one protocol deviation, as determined by sponsor before DBL, will be presented by treatment groups and overall, for all investigational sites combined as appropriate for the study design. An additional summary of participants per major protocol deviation category as well as minor protocol deviation will also be presented. Safety analysis population will be used for participants protocol deviation summary table. Participants may have more than one protocol deviation, which will be counted only once with respect to deviation and deviation category.

The by-participants data listing will be prepared for all protocol deviations.

Document Title:	Statistical Analysis Plan		
Version Number:	Final 1.0	Date:	18Oct2024
Protocol Number:	SARO.17.009	Sponsor Name:	Zydus Therapeutics INC

9.4 Baseline Characteristics

9.4.1 Demographic Data and Other Baseline Characteristics

Demographic and baseline characteristics will be summarized descriptively by the treatment group and by overall for the Safety, mITT and PP populations.

Descriptive summaries will be provided for the demographic and baseline characteristics. Demographic characteristics such as age, gender, race, ethnicity, baseline height, baseline weight, baseline waist circumference, baseline Body Mass Index (BMI), reproductive status, history of significant emotional problems, history of ovarian dysfunction, history of alcohol intake and hirsutism score will be summarized and tabulated for all the analysis populations. All the continuous variables (i.e., age, height etc.) will be summarized by n, mean, standard deviation, minimum, median and maximum values. All the categorical variables (i.e., gender, race etc.) will be summarized as frequency count (n) and percentage (%).

A by-participants data listing for all demographic and baseline characteristics data for randomized participants will be provided. Safety analysis population will be used for by participants data listing.

9.4.2 Medical History

Medical history findings will be coded using the latest version of the Medical Dictionary for Regulatory Activities (MedDRA), and will be presented by Primary System Organ Class (SOC), and by Preferred Term (PT) within SOC.

The number (n) and percentage (%) of unique participants with at least one medical history finding will be presented by default summary statistics. In addition, the number (n) and percentage (%) of participants with at least one medical history finding within each primary SOC, and PT, will be presented by treatment group for all centers combined. Safety analysis population will be used for Medical History summary table. Participants may have more than one medical history, will be counted only once with respect to Primary System Organ Class, and by Preferred Term within SOC.

A by-participant listing of medical history information will be provided for safety population.

9.5 Prior and Concomitant Medications

Medications are classified according to active drug using substances latest version of the World Health Organization Drug Dictionary WHODrug (Global).

Prior medications are defined as medications that started and ended prior to the first administration of study drug. Concomitant medications are defined as medications started on or after first administration of study drug and include medications started prior to the first administration of study drug but continued during the study.

A summary for the frequency and percentage of participants who had previous therapies/medications and a separate summary of participants who had concomitant therapy/medications according to the WHODrug Global primary ATC level 3 subgroup, Preferred Name will be provided treatment group for safety

Document Title:	Statistical Analysis Plan		
Version Number:	Final 1.0	Date:	18Oct2024
Protocol Number:	SARO.17.009	Sponsor Name:	Zydus Therapeutics INC

population. If a medication codes to the ATC level 2 only, the ATC level 2 will be presented in the table in place of the ATC level 3 subgroup.

A by-participant data listing of all prior and concomitant medications including the reported term, Preferred Name, ATC level 3 term (ATC level 2 term, if ATC level 3 is missing), start dates, stop dates and other relevant data will be provided for safety population. Each medication included in the data listing, will be flagged to indicate whether it was a prior or concomitant medication.

9.6 Extent of Exposure and Compliance

Study duration is defined as the date of last visit minus date of informed consent date plus one. Treatment duration is defined as the date of last dose administration minus the date of the first dose administration plus one. If the date of last dose is not available, the date of the last visit will be used in the calculation. If the date of first dose is not available, the date of first study drug dispensation will be used in the calculation. Study duration and the treatment duration will be summarized descriptively by treatment groups for overall study.

Total IP compliance as collected on CRF, will be summarized descriptively by treatment groups. In addition, a categorical summary of compliance will also be presented using the following categories: < 80%, 80% to 120% and >120%. A participant is considered to be compliant if participant takes $\geq 80\%$ but $\leq 120\%$ of the study drug during the study treatment period. Safety analysis population will be used for extent of exposure and compliance summary table.

A by-participant data listing of all information related to exposure and compliance relevant data will be provided for safety population.

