7.1 Overview

This is a Phase 2A, randomized, multi-center, double-blind, placebo-controlled study to evaluate the efficacy and safety of Saroglitazar Magnesium in women with well characterized polycystic ovary syndrome (PCOS) meeting pre-specified inclusion/exclusion criteria. Female participants aged 18 to 45 years will be enrolled in this study across USA and Mexico. Approximately 90 participants who meet the inclusion and exclusion criteria will be randomized in a 1:1 ratio to have 45 Participants in each arm i.e., Saroglitazar Magnesium 4 mg tablets and placebo.

The study will be conducted over a period of up to 34 weeks. Participants will be evaluated at study sites for 8 scheduled visits: (screening (Visit 1: Day [-28], Visit 2: Day [-14 to -7]), randomization (Visit 3: Week 1, Day 1), Visit 4 (Week 2, Day 14), Visit 5 (Week 8, Day 56), Visit 6 (Week 12, Day 84), Visit 7 (Week 16, Day 112) and Visit 8 (Week 24, Day 168). After completion of the study treatment period, the participants will be followed for an additional period of 6 weeks without any study medication until Visit 9 (Week 30, Day 210).

A total of 12 completed participants (6 participants in each treatment group) are planned to be included in the pharmacokinetic assessment. Additional participants may be enrolled into the study to ensure that the pharmacokinetic assessment is performed on at least 6 completed participants in each treatment group.

Note: PK analysis details are not reported in this document, a separate pharmacokinetics analysis plan will be prepared.

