7.2 Study Methodology

Pre-Screening:

An informed consent will be obtained from the potential participants before any pre-screening evaluations. The evaluation of the ALT levels during the pre-screening will be done at the local laboratory, whereas the laboratory evaluations during the screening and the treatment phase will be done at the central laboratory.

Screening Phase:

The screening phase will consist of 28 days. Unless otherwise specified, screening procedures may be completed at any time during the screening phase. Before each participant is enrolled to the study, informed consent will be obtained from the participant (or her legally authorized representative) according to the regulatory and legal requirements of the participating country. Participant eligibility criteria for participation in the study will be assessed. Participants will undergo a serum pregnancy test. During this phase participant will be seen by the investigator or designated study personnel and an AUDIT questionnaire will be administered.

Randomization and Treatment Phase:

The randomization and treatment phase will include 6 outpatient visits (Visit 3 to Visit 8) over a period of 24 weeks including the randomization visit. All the eligible participants will be randomly assigned into either of the two treatment arms: Saroglitazar Magnesium 4 mg tablets and matching placebo tablets in a 1:1 ratio. Efficacy assessments will be conducted at Visit 6 Week 12 and Visit 8 Week 24 visits. In addition,

Document Title:	Statistical Analysis Plan		
Version Number:	Final 1.0	Date:	18Oct2024
Protocol Number:	SARO.17.009	Sponsor Name:	Zydus Therapeutics INC

participants will be monitored during the study and at every visit for development of any adverse events including drug induced liver injury. In addition to physical examination, laboratory data and ECGs done during the study period will be monitored to detect any treatment emergent adverse events.

Safety Follow-up Visit:

A final post-treatment visit will occur 6 weeks (± 3 days) [i.e. Visit 9 Week 30] after the end-of-treatment visit (i.e. Visit 8 Week 24) for safety monitoring. A telephonic follow-up visit will be performed to assess any AE or SAE after the end-of-treatment visit for safety monitoring. As far as possible, all assessments scheduled for end-of-treatment must be performed on all participants who receive the study drug but do not complete the study according to protocol.

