8.3 Definitions

In the following table, the required definitions and calculation for derivation during the analysis are summarized.

Document Title:	Statistical Analysis Plan		
Version Number:	Final 1.0	Date:	18Oct2024
Protocol Number:	SARO.17.009	Sponsor Name:	Zydus Therapeutics INC

Term	Definition / Way of Calculation
Baseline	Baseline is defined as the last non-missing observation (including scheduled and unscheduled assessments within the pre-treatment period) prior to the first dose administration of study drug.
Change from Baseline	Post Baseline Value - Baseline value.
Percentage Change From Baseline	$\frac{(\text{Post Baseline} - \text{Baseline})}{\text{Baseline}} \times 100$
Treatment Start Date/time	Date/time of first dose administration in the study.
Treatment End Date/time	Date/time of last dose administration in the study.
Treatment Emergent Adverse Event (TEAE)	Treatment-emergent AEs are defined as any AE that started after the first dose of study drug or started before the first dose but increased in severity or frequency after administration of the initial dose of study drug.
Duration of Treatment (Days)	Treatment End Date – Treatment Start Date + 1.
Duration of Study (Days)	Last Visit Date – Informed Consent Date + 1.

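### The fallback for a missing last-dose date is not restricted to on-treatment visits, so off-drug follow-up can be counted as treatment duration

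*SAP*

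**What the plan says.** SAP 9.6 gives the definition: "Treatment duration is defined as the date of last dose administration minus the date of the first dose administration plus one". SAP 8.3 is consistent with it and sets the treatment end as "Date/time of last dose administration in the study".

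For a missing last-dose date, SAP 9.6 adds: "If the date of last dose is not available, the date of the last visit will be used in the calculation". SAP 8.3 has no rule that narrows or overrides this.

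The same paragraph of SAP 9.6 uses the same term to close the study period: "Study duration is defined as the date of last visit minus date of informed consent date plus one".

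The visit schedule in SAP 7.1 puts the end of treatment at Visit 8, Day 168: "Visit 7 (Week 16, Day 112) and Visit 8 (Week 24, Day 168". After that, women are "followed for an additional period of 6 weeks without any study medication until Visit 9 (Week 30, Day 210". SAP 7.2 describes this contact as follows: "A final post-treatment visit will occur 6 weeks (± 3 days) [i.e. Visit 9 Week 30] after the end-of-treatment visit (i.e. Visit 8 Week 24".

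**The concern.** The date standing in for the last dose can fall in a period that the SAP itself describes as free of study medication. Time off drug would then be reported as time on drug, against the SAP's own definition of treatment end.

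Two groups are exposed to this:

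- **Completers** who attend follow-up and have no recorded last-dose date.
- **Women who stop early** and remain under observation. Protocol 4.4, 4.4.1 and 4.5 ask for continued follow-up after study drug is stopped. A woman withdrawn from drug for safety could therefore appear to have been treated for longer than she was.

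At stake is the accuracy of the treatment-duration summary by arm and of the by-participant exposure listing.

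**Working it through.** **Inputs**

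- First dose: Day 1 (Protocol 7.2, Visit 3).
- End of treatment: Visit 8, Day 168 (SAP 7.1). Study drug is given on site at scheduled visits (SAP 7.6), so a completer's last dose falls on about Day 168.
- Final follow-up: Visit 9, Day 210 (SAP 7.1), with a window of ±3 days (SAP 7.2).
- Duration = end day − first-dose day + 1 (SAP 9.6).
- Recruitment closed at 60 women (SAP 7.3 and 8.5), randomized 1:1. An equal split of 30 per arm is assumed.

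**Step 1. Reproduce the plan's follow-up length.** 210 − 168 = 42 days, and 42 / 7 = 6 weeks, as stated. The overall length also agrees: 4 weeks of screening + 24 of treatment + 6 of follow-up = 34 weeks.

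**Step 2. Completer with no last-dose date.**

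- By the definition: 168 − 1 + 1 = 168 days.
- By the fallback, with Visit 9 as the last visit: 210 − 1 + 1 = 210 days.
- Excess: 210 − 168 = 42 days; 42 / 168 = 25%.

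Across the Visit 9 window:

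| Visit 9 day | Fallback duration (days) | Excess (days) | Excess (%) |
|---|---|---|---|
| 207 | 207 | 39 | 23.2 |
| 210 | 210 | 42 | 25.0 |
| 213 | 213 | 45 | 26.8 |

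**Step 3. Early stopper.** The documents do not fix her last contact date, so these are illustrations:

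- Last dose Day 56, last seen 42 days later: 98 days instead of 56, an excess of 42 (42 / 56 = 75%).
- Last dose Day 84, followed to Day 210: 210 days instead of 84, an excess of 126 (126 / 84 = 150%).

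**Step 4. Effect on an arm mean.** With 30 women in the arm, each affected completer adds 42 / 30 = 1.4 days. Two add 2.8 days and three add 4.2. The documents do not say how many last-dose dates are missing, so these counts are assumptions.

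**Step 5. What depends on treatment duration.**

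- Adverse events are reported as event counts, participant counts and percentages of participants (SAP 9.8.1). No person-time rate is planned.
- The treatment-emergent window runs from first exposure until the participant leaves the study (SAP 9.8.1), so it does not use the last-dose date.
- Compliance is taken as recorded on the CRF (SAP 9.6), so the 80% to 120% condition for the per-protocol set does not use it either.
- What remains is the descriptive duration summary and the exposure listing.

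**The case against.** **The term is not defined.** SAP 7.1 counts eight scheduled visits at study sites, the eighth being Visit 8, and SAP 7.2 mentions a telephone follow-up. A programmer could take the last attended visit to be Visit 8, and the completer problem would disappear. This stands in part: the SAP never says that Day 210 is the fallback date. But Visit 9 is numbered, SAP 7.2 calls it the final post-treatment visit, and the same paragraph of SAP 9.6 uses the same term to end study duration. Visit 9 is the more natural reading, and two defensible readings are themselves a reason to settle the wording.

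**The completer case should be rare.** At scheduled visits qualified staff give the dose and record it in the eCRF (Protocol 5.10, SAP 7.6). A woman who attends Visit 8 should have a documented dose that day. This stands.

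**The safety results might seem to be distorted.** A reader might infer that exposure is the denominator for the safety data. The documents do not support that: no planned adverse event analysis divides by treatment duration, as Step 5 shows.

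**The error might seem always to run upward.** A reader might infer this too, but it does not follow. A woman lost to follow-up takes dispensed tablets home, so her last dose may come after her last visit and the fallback would understate her exposure. She is a plausible case for a missing date, and for her the last visit is a reasonable substitute. The error is upward only where the last visit is off drug.

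**Conclusion.** The point holds as a minor wording fault. SAP 9.6 allows a missing last-dose date to be replaced by an off-drug visit date. On the natural reading, an affected completer gets about 210 days instead of 168: 42 days too many, 39 to 45 across the visit window, or about 25%. The excess for an early stopper depends on how long she was followed and can be larger.

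This rests on taking Visit 9 as the last visit, on a first dose on Day 1, and on a completer's last dose falling on about Day 168. The 1.4 days on an arm mean per affected completer also assumes 30 women per arm. How many women would be affected cannot be known from the documents and is probably few.

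The consequence is confined to the treatment-duration summary and listing. The primary analysis, the per-protocol set, compliance, the adverse event percentages and the treatment-emergent window are untouched.

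**What to change.** Replace the fallback sentence in SAP 9.6 with a rule along these lines:

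- If the last-dose date is missing, use the earliest available of the Visit 8 date, the early-termination (end-of-treatment) visit date, and the last documented study-drug return date.
- If none of these exists, use the last attended on-treatment visit. This keeps a computable duration for women lost to follow-up.
- Never use Visit 9 or any other off-drug follow-up contact.
- Flag imputed dates in the exposure listing, and report in the summary table how many were imputed in each arm.

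The cost is a few lines in the SAP and a flag in the listing. No new data are needed, because visit dates and drug dispensing and return are already recorded (Protocol 5.10). The one drawback is that, for a woman lost to follow-up, the last on-treatment visit may slightly understate exposure, as the current rule already does.

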9.7 Efficacy Analysis

9.7.1 Primary Efficacy Analysis

9.7.1.1 Endpoint

The primary efficacy endpoint is the change from baseline in hepatic fat content at Visit 8 (Week 24) measured by MRI-PDFF.

9.7.1.2 Estimand

The attributes for the primary estimand related to the first primary endpoint are described below:

1. Treatment: The study compares the efficacy of the Investigational Product (i.e., Saroglitazar Magnesium 4mg) versus the Placebo as randomized in 1:1 ratio.
2. Population: The target population is female participants of PCOS with NAFLD, 18 to 45 years of age. Primarily, analysis will be based on the PP population.
3. Variable: The primary endpoint is the “Change in hepatic fat content from baseline to Week 24” measured by MRI-PDFF.
4. Intercurrent Events:

Document Title:	Statistical Analysis Plan		
Version Number:	Final 1.0	Date:	18Oct2024
Protocol Number:	SARO.17.009	Sponsor Name:	Zydus Therapeutics INC

- Missing Data: Participants may discontinue the study treatment before completing the Visit 8 (Week 24) period, might miss the Week 24 MRI-PDFF measurement, will be considered as missing. The missing data values may be imputed for primary endpoint analysis to consider the analysis treatment effect assuming all participants completed treatment as planned.
- Rescue/Concomitant medication: Participants might require additional treatments (rescue medication or concomitant medications) during the treatment period. The effect of the study treatment will be evaluated regardless of the rescue or concomitant medication.
- Change in ALT inclusion criteria: Participants recruited before the amendment may not fulfill the ALT inclusion criteria due to absence of inclusion criterion. A selection bias will be handled by conducting sensitive analysis, for analyzing subgroup treatment difference (within stratum) based on the ALT score, which will lead to assess whether the change in inclusion criteria has influenced the treatment effect. OR adjustment of the covariates for ALT levels can be performed.

5. Population Level Summary:

The primary efficacy endpoint, the change from baseline in hepatic fat content at Visit 8 (Week 24) will be analyzed using an analysis of covariance (ANCOVA) model. The effectiveness of the investigational product (Saroglitzazar magnesium 4 mg) will be achieved using the lower bound of the 95% confidence interval of the LS Mean difference between the treatment groups.

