7.5 PROTOCOL DEVIATION

For the purposes of this study, no distinction will be made between Protocol Violations and Deviations. Deviations may be categorized as minor protocol deviation and a major protocol deviation. Minor protocol deviation includes any deviations that do not influence the outcome of the efficacy and safety endpoints. Minor protocol deviations do not require immediate notification to the IEC/IRB unless otherwise specified by IEC/IRB requirements. All minor protocol deviations will be noted in monitoring reports and provided to the investigator. Major protocol deviation includes any violation which may influence the outcome of the efficacy or safety endpoints. Major protocol deviations must be reported immediately to the IRB/IEC as specified by the IRB/IEC requirements. All Major protocol deviations will be reported to the Sponsor immediately. Note: persistent non-compliance of minor protocol deviations may rise to the level of major protocol deviations. The Sponsor reserves the right to terminate the study at a given center in the event of monitoring and/or auditing findings of serious or persistent non-compliance with the protocol, standard operating procedures (SOPs), GCP, and/or applicable regulatory requirement(s) by an investigator/institution. In all cases of site closure due to protocol deviations, the IEC/IRB and regulatory authority will be informed. The clinical study report will provide the list of protocol deviations/violations on separate section. Protocol deviation/violation will include but are not limited to the following;

- Subjects that did not meet entry criteria
- Subjects that developed withdrawal criteria but were not withdrawn
- Subjects that received the wrong treatment or incorrect dose
- Subjects that received an excluded medication

Approved by: [name]	Protocol No. SARO.17.009 Version No.: 5.0
------------------------------------	--

 Zydus Discovery DMCC	CLINICAL TRIAL PROTOCOL Saroglitzaz Magnesium – Phase 2A SARO.17.009	Confidential Page 60 of 82
--	--	-------------------------------

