8.4.2 Planned Analysis

All efficacy analysis will be based primarily on the PP population and analysis based on mITT will be considered as supporting analyses for this proof of concept study.

The PP population is a subset of mITT population. The PP population will consist of all randomized patients completing the treatment phase and have not deviated from or violated the protocol in such a way that could affect efficacy outcome (i.e., had both baseline and end-of-treatment MRI & has taken $\geq 80\%$ and $\leq 120\%$ of the study drug).

The mITT population will consist of all randomized patients who received at least 1 dose of the study drug and have at least 1 post-baseline efficacy data. Last observation carried forward method will be used as an imputation method for post-baseline missing values for mITT analysis.

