8.5 HANDLING OF MISSING DATA

Clarifications, wherever possible, will be obtained from the respective Investigator for any missing data or for any illegible entry, unused or unauthenticated data and this will be recorded in the data handling report before the final database lock.

Subjects who are discontinued from the study will be excluded from PP population. Any randomized subject who discontinued the study for any reason but have at least 1 post-baseline efficacy data will be included in the mITT population. Last Observation Carried Forward method will be used as an imputation method for the efficacy variables for mITT population.

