8.2 Analysis Populations

Participant evaluability and their impact on analysis populations will be determined prior to locking the database.

Analysis Population	Definition
Safety (SAF)	The Safety (SAF) analysis population will consist of all participants who: - Were Randomized, - Had administered at least one dose of investigational product.
Modified Intention to Treat (mITT)	Modified Intention to Treat analysis population will consist of all participants who: - Were randomized, - Had administered at least one dose of investigational product - Have at least 1 post-baseline efficacy data of primary outcome.
Per Protocol (PP)	The Per Protocol (PP) analysis population will consist of all participants who: - Were in mITT analysis population, - Completed the treatment phase (i.e., Had both baseline and end-of-treatment primary efficacy outcome & has taken $\geq 80\%$ and $\leq 120\%$ of the study drug) - Have no protocol deviations that could affect primary efficacy outcome.

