9.7.1.3 Analysis Strategy

Primary analysis will be primarily based on the PP population and analysis, based on mITT population with missing value imputation for primary endpoint will be considered as supportive analyses.

The primary efficacy endpoint in this study is the change in hepatic fat content from baseline following 24 weeks of treatment measured by MRI-PDFF. The change from baseline of hepatic fat will be determined as (Visit 8 [Week 24] value – Baseline value).

The actual values observed and change from baseline values of hepatic fat content will be summarized using the number of non-missing observations (n), mean (Mean), standard deviation (SD), median, minimum (Min) and maximum (Max) by treatment groups for baseline and scheduled all visits (i.e. baseline to Week 24 visits).

To check the mean significance difference between baseline and scheduled visit for Week 24, a paired t-test at 5% level of significance will be used.

Following sample SAS code will be used for paired t-test:

```
proc ttest data=data sides=2 alpha=0.5;
paired BASE*AVAL;
run;
```

Where AVAL: variable with post baseline value; BASE: variable with baseline value.

Document Title:	Statistical Analysis Plan		
Version Number:	Final 1.0	Date:	18Oct2024
Protocol Number:	SARO.17.009	Sponsor Name:	Zydus Therapeutics INC

The primary efficacy endpoint, the change from baseline in hepatic fat content at Week 24 will be analyzed using an analysis of covariance (ANCOVA) model. The model will include change in the hepatic fat content values from baseline as dependent variable, treatment group as a fixed effect and baseline values as a covariate.

The estimate the LS means for treatment groups and its 95% confidence interval, the difference of LS Mean for treatment group (Saroglitzaz magnesium 4 mg – Placebo) and its 95% confidence interval of the difference of LS Mean for treatment group, and p-value to check the significance difference at 5% level of significance will be generated using ANCOVA model.

The following sample SAS code pertains to the ANCOVA analysis:

```
proc mixed data=DATA;
class TRT;
model CHG = BASE TRT/solution;
lsmeans TRT/ stderr pdiff cl alpha=0.05;
ods output diffs = DIFFS lsmeans = LSMEANS;
run;
```

Where, CHG: variable with change from baseline values; BASE: variable with baseline values; TRT: variable with treatment values.

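### The primary per-protocol analysis deletes the discontinuers whom the SAP's own estimand says to impute, so the test that decides success does not estimate the stated quantity

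*SAP*

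**What the plan says.** **Primary set.** Protocol 8.4.2: "All efficacy analysis will be based primarily on the PP population". SAP 9.7.1.3 repeats it ("Primary analysis will be primarily based on the PP population"), and the estimand's Population attribute in SAP 9.7.1.2 names the same set: "Primarily, analysis will be based on the PP population".

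**Who is in PP.** SAP 8.2 requires baseline and end-of-treatment primary outcome values. It also requires that the woman "has taken $\geq 80\%$ and $\leq 120\%$ of the study drug" and meets this condition: "Have no protocol deviations that could affect primary efficacy outcome". Protocol 8.5 adds: "Subjects who are discontinued from the study will be excluded from PP population". Protocol 7.5 lists among deviations "Subjects that received an excluded medication".

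**What the estimand asks for.** SAP 9.7.1.2 gives strategies for three events:
- Missing Week 24 MRI, including after discontinuation: values may be imputed to obtain the effect as if everyone had completed treatment.
- Rescue and concomitant medication: "The effect of the study treatment will be evaluated regardless of the rescue or concomitant medication".
- The change in the ALT entry criterion, which does not matter here.

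**Imputation.** SAP 9.7.1.4 assigns multiple imputation to the primary analysis and likens it to a hypothetical strategy. SAP 8.4 restricts it to mITT, as supportive. SAP 9.7.1.5 lists a PP ANCOVA without imputation and an mITT ANCOVA with it, both as sensitivity analyses.

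**The concern.** An estimand that imputes women who stop treatment cannot be estimated in a set that contains only women who did not stop. The plan therefore states one quantity and tests another.

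The test is a superiority comparison, and SAP 9.7.1.3 ties trial success to it. PP membership is settled after randomisation by events that treatment can influence. Protocol 4.5 stops study drug for liver enzyme, CK, amylase or lipase, eGFR and blood-count findings and for certain graded adverse events. If such exclusions differ between arms in number or in prognosis, the retained groups are no longer comparable, and the estimate and its error rate are affected. Protocol 4.4 asks for end-of-treatment assessments, as far as possible, in women who stop early. The primary analysis may therefore discard MRIs that exist.

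**Working it through.** **1. Estimand against primary set**

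| Event | Estimand (SAP 9.7.1.2, 9.7.1.4) | PP set (SAP 8.2; Protocol 7.5, 8.5) | Relation |
|---|---|---|---|
| Discontinuation or missing Week 24 MRI | Keep and impute as if treatment was completed | Removed | Direct contradiction |
| Prohibited concomitant drug | Ignore | Removed if judged before lock to affect the outcome | Clash, dependent on judgement |
| Permitted rescue or stable concomitant drug | Ignore | Retained (permitted by Protocol 5.8, 5.8.1, 5.8.3.1) | Consistent |
| Compliance outside 80% to 120% | Not mentioned | Removed | Gap |

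On the second row, Protocol 5.8.3 prohibits several drugs because of a potential effect on NAFLD. These are the deviations most likely to be judged relevant to liver fat.

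**2. Can the primary analysis use imputation?** PP requires both MRIs, so it has no missing primary value. SAP 9.7.1.5 confirms that PP has no imputation. The first sensitivity analysis there (PP, ANCOVA, no imputation) is thus the primary analysis again. The second (mITT with imputation) is the supportive analysis already named in SAP 9.7.1.3.

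**3. Does mITT fill the gap?** SAP 8.2 requires a post-baseline value of the primary outcome. Protocol 7.2 lists MRI-PDFF among the Week 24 assessments but not the Week 12 ones. A woman with no end-of-treatment MRI therefore leaves mITT as well, and imputation has almost nothing to act on. The protocol's mITT (8.4.1.2) is wider, since any post-baseline efficacy value qualifies. SAP section 10 does not list this narrowing among its changes.

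**4. Form of the bias.** In one arm let a fraction p be excluded, with mean change m_e, and let the retained mean be m_r.

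Full-arm mean = (1 − p)·m_r + p·m_e, so m_r − full-arm mean = p·(m_r − m_e).

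The bias in the treatment difference is this term in the active arm minus the same term in the placebo arm. If placebo exclusions are unrelated to outcome and excluded active-arm women do D points worse than retained ones, PP is too favourable by p × D. For discontinuers under the stated strategy, m_e is the outcome they would have had on completed treatment, which is not observed.

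**5. Scale for an illustration.** An SD is needed. The plan's 37 per arm (difference 4, 80% power, two-sided 5%, t-test) does not follow from its printed SD of 0.6, which gives 2 per arm. An SD of 6 gives 37 per arm (power 80.8%). SD 6 is therefore an assumption. SAP 8.5 closes recruitment at 60, or 30 per arm.

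**6. Illustration with no true effect.** Assume equal exclusion rates in both arms and placebo exclusions unrelated to outcome. SE = 6 × √(2/n); at n = 24 this is 1.73. The error rate is one-sided, nominal 2.5%, in the direction of fat reduction. (The success rule as worded in SAP 9.7.1.3 points the other way, which is a separate matter.)

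| Excluded | n per arm | D | Bias = p × D | Error rate |
|---|---|---|---|---|
| any of 10%, 20%, 30% | 27, 24, 21 | 0 | 0 | 2.5% |
| 10% | 27 | 3 | 0.3 | 3.8% |
| 20% | 24 | 3 | 0.6 | 5.3% |
| 20% | 24 | 6 | 1.2 | 10.0% |
| 30% | 21 | 6 | 1.8 | 15.6% |

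The documents give neither D nor a PP exclusion rate. The 20% in the sample-size section is an assumed dropout rate, not a PP exclusion rate.

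**The case against.** **PP was chosen openly.** The protocol named it as primary for a proof-of-concept study, with mITT as supportive, and the estimand's Population attribute repeats it. This stands as far as it goes: the choice is neither hidden nor post hoc. It does not reconcile the text. If the population is defined by the absence of discontinuation, a strategy for discontinuation has nothing to act on. The inconsistency then lies inside the estimand itself.

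**SAP 9.7.1.4 may mean the primary endpoint rather than the primary analysis.** That would agree with SAP 8.4. The stated strategy would then be carried out only in a supportive analysis, whose set excludes most of the women it is meant for.

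**Three stronger readings are tempting, and the documents do not support them.**
- A reader might infer that rescue or concomitant medication in general removes women from PP. It does not: rescue and stable concomitant drugs are permitted, and the PP rule does not name excluded drugs.
- A reader might call the compliance rule a contradiction of the estimand. The estimand does not list non-compliance, so this is an omission.
- A reader might compute that, with 20% excluded and gaining nothing, a PP effect of 4 points means 4 × 0.8 = 3.2 overall, a 25% overstatement. That measures PP against a treatment-policy target for discontinuers. The SAP states a hypothetical one, under which zero benefit in discontinuers is not the quantity sought.

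**Conclusion.** The point holds for discontinuation and missing MRI: the primary analysis cannot estimate the SAP's estimand, and it conditions on post-randomisation events. It holds in a limited form for prohibited drugs judged to affect the outcome. The compliance rule is a further post-randomisation exclusion that the estimand leaves unaddressed. Neither the current mITT analysis nor the listed sensitivity analyses would reveal a problem.

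The size is unknown. The documents do not show that the result will be biased or that the error rate is inflated. They show only that the plan gives no protection if excluded and retained women differ. The illustrative error rates rest on SD 6, 30 per arm, equal exclusion rates and outcome-related exclusion in the active arm alone. This should be corrected before database lock.

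**What to change.** - Make the primary set all randomised women who took at least one dose, analysed as randomised, without requiring a post-baseline MRI. Keep women in it whatever their compliance or concomitant medication.
- State one strategy for treatment discontinuation. Say whether an off-schedule end-of-treatment MRI counts under that strategy, and specify the multiple imputation to match. Using early scans as they stand and imputing as if treatment was completed answer different questions.
- Add non-compliance to the intercurrent events.
- Make PP supportive, delete the duplicate PP sensitivity analysis, and reconcile SAP 8.4, 9.7.1.4 and 9.7.1.5.

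Promoting the present mITT set would not be enough, for the reason in step 3 of the working.

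**Cost.** No new data: SAP rewording and some added imputation work before lock. The estimate may be less favourable. Power could move either way. Under SD 6 and a difference of 4, it is 61.8% with 24 per arm and at most 71.9% with 30 per arm and complete data. It is about 54% (normal approximation) if a treatment-policy strategy were chosen and the difference fell to 3.2. If the database is already locked, the SAP introduction requires the change and its reason to be documented in the study report.
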